Hypothesis 1: GV's with CMP assigned to RET will show statistically significant and clinically meaningful improvements in self-reported pain, physical function and PGIC compared to WLC. We also expect significant improvements in the secondary outcomes known to change after exercise training (e.g. sleep, self-esteem, fatigue, anxiety and depression).

Aim2: To determine the influence of RET on total daily physical activity levels using complementary subjective self report and objective measures (accelerometers).

Hypothesis 2: GV's with CMP assigned to RET will show an increase in total physical activity by the end of the trial that is attributable entirely to an increase in RET.

Aim 3: To determine the influence of RET on brain mechanisms of pain **sensitivity** and **regulation** in GV's with CMP compared to WLC. Brain responses to painful heat stimuli will be measured using fMRI. Pain sensitivity will be determined by exposing participants to mild, moderate and strong pain stimuli. Pain regulation will be determined by having the participants perform attention-demanding cognitive tasks while receiving moderately painful stimuli.

Hypothesis 3A (Pain Sensitivity): GV's assigned to RET will show decreased ratings and decreased brain responses to experimental pain stimuli by the end of the treatment trial compared to baseline.

Hypothesis 3B (Pain Regulation): By the end of the treatment trial, GV's assigned to RET will show **decreased** brain responses in areas that process the sensory aspects of pain (e.g. cingulate & sensory cortices), and **increased** brain responses in areas that modulate or inhibit pain when diverting their attention away from a painful stimulus compared to baseline.

Aim 4: To determine the influence of RET on pain-relevant brain white matter tracts in GV's with CMP compared to WLC by conducting DTI analyses of white matter tracts from the thalamus to regions of the brain involved in pain processing and control (e.g. insula, periaqueductal gray, frontal and cingulate regions).

Hypothesis 4A: GV's assigned to RET will show improvements in white matter (measured as increased fractional anisotropy and/or decreased mean diffusivity) compared to baseline.

Research Design and Methods

Pilot subjects:

Five healthy adults (ages 18-60) will be recruited for a single MRI scanning session.

Screening and exclusion criteria for pilot subjects:

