or 49°C) using the Medoc TSA described above. Each temperature will be presented randomly thrice for a total of 9 stimulus presentations, with an inter-stimulus interval of 1 min. Each subject will receive one block of stimuli to the thenar eminence of the left hand during initial sensitivity testing and then be exposed to a second block of 'moderate' stimuli during the Stroop/Pain run of the MRI simulation. Baseline temperature will be set at 32°C. The temperature will increase at a rate of 40°C per sec until the desired temperature for that particular stimulus is achieved. The target temperature will be sustained for 20 sec and then decreased at a rate of 40°C per sec. Painful heat will be rated on two separate category-ratio scales (64). One scale will assess intensity and the other unpleasantness. Each scale contains 12 verbal descriptors aligned to numeric ratings ranging from 0 to 20. Subjects will rate the intensity and unpleasantness immediately following each temperature. Category-ratio pain scales have established validity and reliability for assessing experimental pain stimuli and provide data necessary to create psychophysical curve estimates (65). The pain intensity ratings from the randomly presented stimuli will be used to establish each participant's individual temperature used to elicit the moderate pain ratings during fMRI scanning. The three absolute thermal stimuli (45°C, 47°C, and 49°C) will be used throughout the trial and pain ratings to them will serve as the primary outcome variable for pain sensitivity. The total number of 20-second thermal stimuli for the simulation will not exceed 18. In the interest of comfort and safety, at least one member of the study staff will be with the subject in the MRI simulator room at all times. Subjects will be informed that if at any time during testing they feel they can no longer tolerate the stimulus, they should verbally indicate as much and we will immediately halt the stimulation procedure and remove the thermode from their hand. The Medoc TSA devices are equipped with an emergency stop on the front panel of the unit. In addition, any stimulation procedure in progress can be immediately interrupted with a keyboard shortcut (hitting the "S" key) on the laptop which runs the TSA software. In the event that a stimulation procedure is interrupted, either by use of the emergency stop or keyboard shortcut, the face of the thermode will revert to the default baseline temperature, 32°C.

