Our experience and data in CMP patients show that MRI habituation procedures are effective to screen for claustrophobia, deliver relative pain stimuli, enhance task performance and minimize subject motion. MRI habituation will take place in the MRI simulator at Waisman. This will entail being placed in a mock MRI unit, trained to rate painful stimuli, and perform the cognitive tasks (Stroop) using the same equipment that will be used in the 3T MRI unit. Pain psychophysics are also conducted and used to calculate the temperature designed to elicit moderate pain ratings. We have found that by habituating subjects they report feeling more at-ease in the MRI which should enhance measurement reliability. Our motion parameters indicate that by habituating subjects' data loss due to motion artifact is limited. In our FM study, quality data analyses indicate that only 6 of 100 subjects had motion exceeding 3 mm. The mock MRI is virtually identical to the actual MRI including fed-in scanner noise. Subjects practice with a scanner-compatible button-press response unit (Current Designs Inc., PA) while viewing stimuli through MRI compatible goggles.

Physical Activity Assessment

Baseline physical activity assessment will occur for one week prior to baseline brain imaging using an accelerometer. Physical activity will also be assessed for one week prior to each testing session. Subjects will be given instructions on the proper use of the accelerometer and will be asked to wear it as much as possible, unless sleeping, bathing or swimming, for the week preceding their baseline assessment.

Baseline Assessment and 16-Week Trial (RET vs. WLC)

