To estimate the impact of RET on BOLD responses to pain stimuli we will use a two-sample Hotelling's T-square approach. This will test differences in the vector of means of BOLD response from pain stimuli for the control and exercise group between the baseline (before treatment) and end of the study (after treatment) for three different brain regions (anterior cingulate, insula and middle frontal cortices). These regions were chosen based on the robust brain responses observed in patients with CMP. Hotelling's T-square is a generalization of the Student's t statistic that is used in multivariate hypothesis testing. If there are q variables, the null hypothesis is that the means of variables in the first population equal the means of variables in the second population. For each subject in each group the difference between baseline value and end of the trial value for all brain regions will be computed and a Hotelling's T-square will be performed to compare the mean difference vectors for each group. With a sample size of 34 subjects we will have 80% power to detect a moderate effect size ($\sim .6$), in the treatment group, between baseline and the end of the trial.

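### Hypothesis 3B judges pain regulation on the response during distraction alone, so its sensory-area half cannot be told apart from lower pain sensitivity

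*Combined protocol and SAP*

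**What the plan says.** Specific Aims and Hypotheses, Aim 3, names sensitivity and regulation as two things to be measured. For the second: "Pain regulation will be determined by having the participants perform attention-demanding cognitive tasks while receiving moderately painful stimuli". That definition has no undistracted reference. Under Hypothesis 3A, trained veterans "will show decreased ratings and decreased brain responses to experimental pain stimuli by the end of the treatment trial compared to baseline". Hypothesis 3B predicts, during distraction, a fall in areas handling the sensory side of pain and a rise in "brain responses in areas that modulate or inhibit pain when diverting their attention away from a painful stimulus compared to baseline".

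The moderate stimulus is set individually. Under Day 1 (Screening Day), ratings of the 45, 47 and 49°C stimuli "will be used to establish each participant's individual temperature used to elicit the moderate pain ratings during fMRI scanning", and of the simulator session the same section says: "Pain psychophysics are also conducted and used to calculate the temperature designed to elicit moderate pain ratings". The three absolute temperatures are to be used throughout the trial. For the individual temperature, the Study Schedule and the sections on the 16-week trial and on follow-up describe no recalibration, but they do not say that it is held either.

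In Statistical Considerations, a Hotelling's T-square compares the two arms' baseline-to-end changes in anterior cingulate, insula and middle frontal cortex: "This will test differences in the vector of means of BOLD response from pain stimuli". The secondary imaging paragraph powers pain and pain plus distraction as separate main effects. The mixed models for BOLD and DTI name no contrast between those conditions. Heat alone is set against heat with the task only under Pilot Scans, in five healthy adults.

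**The concern.** Regulation by distraction is a difference: how much less pain, or how different a brain response, a person has when attention is diverted than when it is not. The background section on attention and distraction takes that view, since it expects training to make veterans better at distracting themselves from pain. Hypothesis 3B measures only one side of the difference. If training makes a given heat less painful, the response falls with or without the Stroop task, and the sensory-area half of 3B follows from 3A. A reader of the results could then credit regulation with a change that belongs to sensitivity, and no planned contrast would show otherwise.

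**Working it through.** **The plan's own figure.** Statistical Considerations gives 80% power with 34 subjects and an effect of about 0.6 in the treatment group from baseline to end. A one-sample Hotelling's T-square with n = 34, q = 3 regions, joint (Mahalanobis) distance 0.6 and alpha 0.05 (stated for Aim 1 only; assumed here) has noncentrality 34 × 0.36 = 12.24 on F(3, 31). Its power is 0.795, so the figure reproduces. A two-arm T-square with 34 per arm gives 0.500 at the same joint distance, or 0.796 if each region shifts by 0.6 with an assumed inter-region correlation of 0.3. On every reading, the power is for a simple change in response to pain stimuli. It does not apply to a contrast that isolates regulation.

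**Algebra.** Let P be the change in response to pain alone and D the change during pain plus distraction. Suppose training lowers sensitivity by d in both conditions and leaves regulation unchanged. Then P = −d, D = −d and D − P = 0. The measure in 3B shows the fall and the contrast shows none. The wait-list arm does not help, because a fall caused by training occurs only in the trained arm.

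**Illustration.** The settings were 20,000 simulated trials, 34 per arm (Subjects section) and two-sided 5% tests, counting significant results in the lower direction. The following are assumed and not in the documents: change-score SD 1, and correlation r between P and D of 0.3 to 0.8 for the first row and 0.6 for the others.

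| Scenario | D only, between arms | D only, within training arm | D − P, between arms | D − P, within training arm |
|---|---|---|---|---|
| Sensitivity falls 0.6 SD, equal shift | 68–69% | 92–93% | 2.3–2.6% | about 2.5% |
| Sensitivity falls 0.3 SD, equal shift | 23% | 39% | 2.5% | 2.6% |
| Proportional fall: P −0.6, D −0.42 | 40% | 66% | 0.2% | 0.1% |
| Regulation only: D −0.6 | 68% | 93% | 77% | 97% |

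The first and last rows are nearly identical on the distraction-only measure, so that measure cannot distinguish them; the contrast can. The analytic power of a t-test at 0.6 SD (0.684 between arms, 0.924 within one arm) agrees with the first row.

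**Precision.** With equal variances, Var(D − P) = 2(1 − r) Var(D). This is 1.0 × Var(D) at r = 0.5 and 0.8 × Var(D) at r = 0.6. The contrast is noisier only when r is below 0.5.

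**Scale.** In the proportional row the response under distraction is assumed to be 70% of that without it, so D = 0.7 × (−0.6) = −0.42 and D − P = +0.18. The contrast shrinks although the relative relief is unchanged. It gives no false support for 3B, but it leans against it.

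**The case against.** The strongest reply is that 3B joins two predictions. A general fall in sensitivity predicts lower responses; it does not predict an increase in modulatory areas, so the second half of 3B helps to separate the two explanations. This stands. A reader might infer that the trial cannot answer the regulation half of Aim 3, or would report improved regulation whenever sensitivity fell. The documents do not support that, because 3B as worded would not be met. However, no planned test enforces the conjunction: Hotelling's T-square is non-directional across its three regions.

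A reader might also infer that habituation to repeated heat explains a fall from baseline. The hypotheses do refer to baseline, but Aim 3 is framed against the wait-list arm, both arms attend the same test visits, and the T-square compares the arms' mean changes. Habituation common to both arms is therefore handled.

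Third, the temperature may be reset at each visit so that it stays moderately painful. That is possible. A fixed temperature is the natural reading, but it is not stated. Resetting would shrink the confound while making the physical stimulus differ between visits.

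Finally, the contrast is not clean. It carries activation from the Stroop task itself, and the background section reports that parts of the anterior cingulate respond to Stroop and to pain independently and that exercise improves attentional control. That also stands and limits how cingulate and frontal results can be read.

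**Conclusion.** The concern holds in a limited form. As specified, a fall in the sensory areas during distraction cannot be attributed to regulation, and the wait-list comparison does not repair this. The conclusion depends on training lowering sensitivity and on the moderate temperature being kept from Day 1. Under an equal shift of 0.6 SD with no change in regulation, the sensory-area half would be met in about 68% of trials between arms and about 92% within the trained arm; at 0.3 SD the figures are 23% and 39%. The effect sizes, SD and correlations are assumed, so these rates illustrate the logic and do not forecast the trial. It would go too far to say that the whole sensory-area effect would be misattributed. That follows only by construction, when sensitivity alone changes and the shift is additive. The modulatory half of 3B is not threatened in this way, and the trial's main efficacy question under Aim 1 is untouched. This is a cheap improvement to a mechanistic aim.

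**What to change.** Pre-specify as the test of 3B the baseline-to-week-17 change, training versus wait-list, in the within-session contrast of pain plus Stroop minus pain alone at the same temperature, for both BOLD and ratings. Report it beside the distraction-only change. Require both directional parts of 3B before claiming improved regulation. State how the individual moderate temperature is handled at later visits; which rule applies is for the sponsor to decide.

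The cost is a reworded hypothesis and one added contrast. The imaging text indicates that both conditions are scanned, but it does not confirm that each participant's own moderate temperature is also delivered without the task. If it is not, the reference must be derived from the three fixed temperatures, which is simpler for ratings than for BOLD, and the variance formula above would not carry over directly.

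The plan should name three downsides. The contrast includes Stroop-related activation, so cingulate and frontal results need cautious reading. It assumes an additive scale, and a proportional fall in sensitivity would shrink it. It is also noisier if the two conditions correlate below 0.5.

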Following enrollment, subjects will be asked to undergo five phases of testing that will include: 1) a clinical interview and a clinical assessment at the Madison VA hospital; 2) psychophysical and cognitive testing in a mock MRI environment; 3) repeated psychophysical, cognitive, and physical activity assessments as well as functional neuroimaging, which will overlap with; 4) a 16-week resistance training exercise (RET) regimen or wait-list control (WLC) depending on group assignment; and 5) follow-up with test sessions at 6 and 12 months after the completion of primary testing. The clinical interview will occur following written consent and will be completed on the first day of testing in a private office at the VA hospital. A clinical assessment will also occur in a private exam room at the Madison VA following written consent to ensure study eligibility. Upon completion of the clinical interview and assessment, testing will commence and will consist of filling out questionnaires, participating in psychophysical and cognitive performance testing and undergoing MRI environment habituation in a mock MRI. After completing the initial test day and confirming the Veteran's eligibility to continue participation they will be assigned to their condition, either RET or WLC, and scheduled for the baseline MRI scan. We plan to test in cohorts of 12 Veterans, 6 in each condition, by screening individuals over a 1-2 month period and conducting baseline scans for all cohort members over a 2-week period. The RET regimen and WLC will begin the week following the baseline scan and continue for 16-weeks. Veterans in both conditions will make 3 lab visits during the course of the RET/WLC with a fourth lab visit after the 16-week intervention has concluded. Two follow-up lab visits will take place at 6 and 12 months after the completion of the primary testing. A bulleted version of the study schedule appears below:

◆ Pilot testing

- We plan to enroll enough pilot subjects to test the exercise and brain scanning procedures on 5 individuals. Pilot subjects will be asked to complete a modified version of the brain scanning procedures which will include the administration of painful stimuli, cognitive task and perceptual rating.

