 - The first day of testing will occur in the MRI simulator room at the Waisman Laboratory for Brain Imaging and Behavior.
 - Psychophysical pain testing will occur during this session, both before and during the MRI simulation procedure.
 - The cognitive task will be introduced and subjects will be permitted to practice the task. This same task will be employed during the MRI simulation as well as actual scans.
- **Physical Activity Assessments**
 - During the week prior to Day 2 participants will wear an activity monitor which will record intensity and frequency of physical activity
- **Participants are assigned to their experimental condition, either RET or WLC**
 - Participants assigned to the RET group will work with study staff to schedule their training sessions for the 16-week trial.
 - Participants assigned to the WLC group will be instructed to maintain their current level of physical activity and exercise for the 16-week trial.

◆ **Day 2 of Testing**

- **Baseline psychophysical, cognitive and functional brain imaging (to occur within 2 months of the first day of testing)**
 - fMRI data collection during psychophysical pain testing and cognitive performance tasks will occur in the 3T MRI room at the Waisman Laboratory for Brain Imaging and Behavior.

◆ **16-Week Trial (will start approximately 1 week after Day 2)**

- **RET group members will attend twice-weekly training sessions (90 minutes) with a personal trainer at the VA Physical Therapy clinic**
- **Outside of test days, WLC group members will go about their typical daily routine**
- **Both groups will complete a small battery of clinical symptom questionnaires on a weekly basis either at home (WLC) or just prior to a training session (RET)**

◆ **Blood Sampling**

- **RET group members will have blood samples drawn one hour before and thirty minutes following their first training session of the week during weeks 2, 7, and 15.**
 - Total volume of blood drawn over the duration of the study for participants in the RET group will be 240 ml.
- **All blood draws will be conducted by a certified phlebotomist who is also a member of the study staff.**
- **Blood draws will take place in the Exercise Psychology Laboratory at the University of Wisconsin-Madison.**

◆ **Days 3, 4 and 5 of Testing**

- **Psychophysical, cognitive and functional brain imaging data will be collected at weeks 6 and 11 of the 16-week trial and one week after completion (week 17)**

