After the baseline physical activity assessment, Veterans will return for baseline brain imaging including tests of pain sensitivity and regulation and diffusion tensor imaging. As a safety precaution for pain testing during the MRI scan, all subjects will be provided with easy access to a squeeze-bulb alarm in order to interrupt a scan in progress. Subjects will be instructed to use (squeeze) the alarm trigger if they can no longer tolerate the pain stimulus or if they are too uncomfortable in the scanner to continue. Standard procedure for the MRI technicians at the Waisman lab is to immediately stop the scan if the subject triggers the alarm. Likewise, study staff will immediately stop any thermal stimulus protocol in operation should the subject trigger the alarm. If the procedures during a scanning session are interrupted due to an equipment failure, we will end the session and ask the participant to reschedule. Subjects will be paid \$75 and have travel reimbursed for any session ended prematurely for any reason.

Once the first twelve Veterans are screened, baseline tested and assigned to groups we will begin the first 16 weeks of RET and WLC. During RET and WLC protocols, Veterans will be scheduled to return to the Waisman center on weeks 6, 11 and 17 for retesting of the primary and secondary outcomes. The testing will be conducted on the non-exercise training days or prior to exercise on training days to avoid having acute exercise influence the outcomes. Physical activity assessment via accelerometry will always be collected on the week immediately preceding visit to Waisman (i.e. weeks 5, 10 and 16) so that we can determine the relationships between total physical activity, symptoms and brain function and structure. Due to the number of brain scans required, and the availability of the 3T MRI, we plan to test Veterans in small cohorts on the same day. However, should a particular participant fall out of time with their respective cohort, we will test them per the protocol (i.e. at 6, 11 and 17 weeks). During each 16-week cohort, we will be screening, clinically assessing and baseline testing the next cohort of 12 Veterans to begin their 16-week assignment. Veterans will be tested at 6 and 12 months post RET or WLC in order to obtain follow-up symptom, physical activity and brain function and structure data.

Blood Collection

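### Veterans learn their arm at the end of Day 1, before the baseline accelerometer week and the baseline scan, and another section implies the opposite order

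*Combined protocol and SAP*

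**What the plan says.** The Study Schedule narrative places allocation after the first test day and confirmation of eligibility: "they will be assigned to their condition, either RET or WLC, and scheduled for the baseline MRI scan".

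The bulleted schedule lists assignment under Day 1 and shows that it is disclosed:

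- RET: "Participants assigned to the RET group will work with study staff to schedule their training sessions for the 16-week trial".
- WLC: "Participants assigned to the WLC group will be instructed to maintain their current level of physical activity and exercise for the 16-week trial".

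The tests that the schedule labels as baseline come on Day 2, "to occur within 2 months of the first day of testing". The accelerometer baseline is tied to that visit: "During the week prior to Day 2 participants will wear an activity monitor which will record intensity and frequency of physical activity". On what Day 2 contains, the section Baseline Assessment and 16-Week Trial says: "After the baseline physical activity assessment, Veterans will return for baseline brain imaging including tests of pain sensitivity and regulation and diffusion tensor imaging".

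That same section lists the steps in another order: "Once the first twelve Veterans are screened, baseline tested and assigned to groups we will begin the first 16 weeks of RET and WLC".

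The Day 1 (Screening Day) section puts the Aim 1 outcomes, the Aim 2 questionnaire (IPAQ) and a block of heat-pain ratings at 45, 47 and 49°C on Day 1. No section describes withholding the arm until Day 2 or blinding assessors to arm. The confidentiality text only keeps data staff who have no participant contact from knowing whose data they handle.

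**The concern.** A baseline is meant to describe participants before allocation can affect them. Here, a Veteran expecting supervised training and a Veteran told to carry on as usual both enter the accelerometer week and the scan knowing their arm. The plan's own background gives reasons why this could matter. It treats anticipation and attention as determinants of pain, links inactivity in fibromyalgia to fear that exercise will worsen pain, and considers it plausible that taking up training changes other daily activity.

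The baselines concerned are used. The Aim 3 Hotelling test is built on each participant's baseline-to-end difference, Hypotheses 3A, 3B and 4A are worded against baseline, and the Aim 2 analysis names accelerometer counts. A shift at baseline could enter those comparisons in either direction, and it cannot be removed once the data are collected.

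There is also a loss problem. A Veteran who withdraws between assignment and Day 2 has been randomised but has no accelerometer or scan baseline.

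**Working it through.** **Order of events, from the schedule text**

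1. Day 1: consent, clinical assessment, interview, Aim 1 outcomes, IPAQ, first heat-pain ratings in the simulator.
2. End of Day 1: arm assigned; RET books training, WLC receives its instruction.
3. Accelerometer week, ending at Day 2. With 2 months taken as about 61 days, it can start as late as 61 − 7 = 54 days after Day 1, a little under eight weeks.
4. Day 2: scan with pain ratings, BOLD and DTI, at most 2 months after Day 1.
5. About one week later: the 16-week trial starts.

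The baselines at steps 3 and 4 follow step 2. The list in the baseline assessment section would move step 2 to after step 4. Both orders cannot be followed.

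**The plan's nearest figure**

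Statistical Considerations gives 80% power for Aim 3 with 34 subjects and an effect of about 0.6. Take a one-sample Hotelling T-square with q = 3 regions, n = 34, multivariate distance D = 0.6 and alpha 0.05 (assumed to apply here):

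- noncentrality = nD² = 34 × 0.36 = 12.24 on 3 and 31 degrees of freedom; power = 79.5%, which reproduces the stated 80%.
- the two-sample version has noncentrality (n/2)D² = 17 × 0.36 = 6.12 on 3 and 64 degrees of freedom; power = 50.0%.

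So the 0.6 in that statement is a change within the RET arm. The two-sample shortfall is a separate matter. Neither figure depends on when the arm is disclosed.

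**How a baseline shift carries through**

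Let δ be the difference between arms at baseline, in SD units, that arises only because participants know their arm. The reference is the contrast that a pre-allocation baseline would have given.

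- Change score: the observed contrast is end minus (true baseline + δ), so the bias is −δ.
- Baseline as covariate, equal variances, correlation ρ: the bias is −ρδ.

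The plan states ρ = 0.6 for repeated measurements in its Aim 1 sample-size calculation; I assume the same value here. The documents give no δ, so 0.1 to 0.3 SD is an assumption.

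| Assumed δ (SD) | Change-score bias (SD) | Covariate-adjusted bias, 0.6 × δ (SD) |
|---|---|---|
| 0.1 | 0.10 | 0.06 |
| 0.2 | 0.20 | 0.12 |
| 0.3 | 0.30 | 0.18 |

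The change-score column applies to the Aim 3 test as specified. For Aim 2 the plan describes a time-averaged difference and does not say how baseline enters, so the bias there depends on a choice not yet made; if baseline is not used, it is nil. DTI values go into random coefficient mixed models, again without a stated change-score test.

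**The case against.** The strongest reply is that the order is not settled. The Day 1 bullets are not strictly chronological, since the accelerometer week appears above the assignment bullet although it falls after Day 1, and the baseline assessment section puts testing first. That is fair as far as it goes, but it leaves a contradiction to resolve. The narrative independently couples assignment with scheduling the scan, and the scan has to be scheduled before the week that precedes it.

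Several stronger readings might be inferred, and the documents do not support them:

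- *That all baselines for Aims 2 to 4 are taken after allocation.* The IPAQ and a full block of heat-pain ratings are taken on Day 1. The schedule nevertheless labels the Day 2 tests as baseline.
- *That primary efficacy is compromised.* The pain VAS and SF-36 baselines are also taken on Day 1.
- *That every Veteran waits 2 months.* This is a ceiling. Screening runs over 1 to 2 months and scans over 2 weeks, so those screened late may wait much less.
- *That WLC participants are told to restrict activity during the baseline week.* The instruction refers to the 16-week trial. The exposure is knowledge of the arm, since training has not begun.
- *That all of Aims 2 to 4 use change scores.* Only the Aim 3 T-square explicitly does.
- *That the bias is a known fraction of the planned effect.* The size is assumed, and the plan's two 0.6 values belong elsewhere: one to Aim 1, the other to a within-RET change. I therefore do not divide by them.
- *That early withdrawals break the intent-to-treat set.* All randomised subjects stay in the analysis, and missing-data methods are named. Early loss adds missing data; it does not remove anyone from the set.

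It is also fair that no mechanism is evident for knowledge of the arm to alter white matter.

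**Conclusion.** The point holds for the accelerometer and scan-day baselines. Two parts of the schedule put allocation and its disclosure before those measurements, a third implies the reverse, and nothing in the plan protects them from knowledge of the arm. The risk is greatest for wear-week activity and scan pain ratings, lower for BOLD and least plausible for DTI.

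The direction and size of any shift are unknown. On the assumed range, the Aim 3 contrast would be off by 0.1 to 0.3 SD; a baseline-adjusted model at correlation 0.6 would be off by 0.06 to 0.18 SD. Adjustment therefore reduces the bias without removing it. Withdrawals before Day 2 add avoidable missing data.

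This should be fixed because it is avoidable and the text already conflicts. It does not undermine the Aim 1 comparison.

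**What to change.** Reconcile the Study Schedule narrative, the Day 1 bullets and the baseline assessment section so that all three state one order: Day 1 tests, accelerometer week, Day 2 scan, then randomisation and disclosure, then the 16-week trial. Move the booking of RET sessions and the WLC instruction to after Day 2. Veterans who withdraw or prove ineligible before Day 2 are then never randomised.

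The cost is time for booking. Two sessions a week for 16 weeks is 32 individually supervised sessions per RET participant, to be arranged in about a week rather than over as much as 2 months. The flexible and weekend hours already planned should help, and staff could record every Veteran's availability beforehand without revealing an arm. No study visit is added, and the sample size, alpha and power figures do not change.
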